3.2. Study Design

This is a Phase 2b, randomized, double-blind, placebo-controlled, parallel group, multicenter study evaluating the efficacy and safety of SEL in subjects with T2DM and moderate to advanced DKD.

Subjects meeting the study’s entry criteria after signing the informed consent will enroll into a Run-in period of at least 5 weeks and receive at least one week of placebo to match (PTM) and then SEL (18 mg) for at least 4 weeks. After completing the Run-in period, subjects meeting eligibility will be randomized in a 1:1 ratio to receive SEL (18 mg) or PTM orally once daily. Subjects must be on SEL for at least 7 consecutive doses prior to Visit C and Visit 1 in order to randomize.

The overall study design is presented graphically in [Figure 3-1](#).

Figure 3-1. Study Design Schema

- Abbreviations: EOS = End of Study, EOT = End of Treatment, PTM = placebo-to-match to match, SEL= Selonsertib
- Prior to randomization, subjects must have at least 7 consecutive daily doses of study drug immediately prior to Visit C and Randomization (Visit 1)
 - Post-run-in baseline eGFR is defined as the average of Visit C and Visit 1 eGFR values. Pre-run-in baseline is defined as the average of Visit A and Visit B eGFR values.
 - If kidney failure is reached, subjects should discontinue study drug and remain on study.
 - If a subject permanently discontinues study drug, there will be a 30 Day EOT Follow-up visit. Subjects who permanently discontinue study drug prior to the global study end date will have an EOT visit and a 30 Day (± 7 days) EOT Follow-up visit. Subjects are encouraged to complete all remaining study visits until the global study end date.
 - The global study end date will occur when the last randomized subject reaches 48 weeks and/or all subjects on study have completed end of study assessments and the 30 Day EOS Safety Follow-up visit.

Randomization will be stratified by average eGFR values from Visit A and Visit B, average urine albumin to creatinine ratio (UACR) values from Visit A and B, and concomitant use of sodium-glucose co-transporter-2 (SGLT-2) inhibitors at Visit 1.

Subjects will continue to receive SEL or PTM in a double-blind fashion until death, study drug discontinuation, kidney failure (dialysis performed for at least 4 weeks, kidney transplantation, or confirmed decrease in eGFR to $< 15 \text{ mL/min/1.73 m}^2$ for subjects without dialysis or kidney transplantation), or the global study end date.

3.3. Duration of Treatment

At least 52 weeks (4 weeks during the Run-in period and at least 48 weeks post randomization)

3.4. Discontinuation of Study Drug

Selonsertib or PTM should be discontinued for any of the following reasons in consultation with the Gilead Medical Monitor and/or sponsor designee:

- Death
- Kidney failure (dialysis performed for at least 4 weeks, kidney transplantation, or confirmed decrease in eGFR to $< 15 \text{ mL/min/1.73 m}^2$ for subjects without dialysis or kidney transplantation)
- Pregnancy during the study; refer to [Appendix 6](#)
- Participation in another therapeutic clinical study
- Clinically significant adverse event in the opinion of the subject or investigator
- Significant protocol violation that impacts subject safety
- Significant subject noncompliance with study drug administration, study procedures, or study requirements per judgement of the investigator
- Intercurrent illness that would, in the judgment of the investigator, *permanently* affect assessments of clinical status to a significant degree
- Unacceptable toxicity, or toxicity that, in the judgment of the investigator, compromises the ability to continue study-specific procedures or is considered to not be in the subject's best interest
- Study blinding is intentionally broken by the subject or the study site
- Discontinuation of the study at the request of Gilead, a regulatory agency, or an institutional review board or independent ethics committee (IRB/IEC)

Subjects who permanently discontinue study drug will have an end of treatment (EOT) visit scheduled as soon as possible after the decision to discontinue study drug is made. If an ECG, STS was conducted at a previous visit within 24 weeks of the EOT visit, the assessment does not need to be performed at the EOT visit. In addition to the EOT visit, subjects who permanently discontinue study drug prior to global study end date will have a 30 day (± 7 days) EOT Follow-up visit which will include an assessment of eGFR and UACR.

Every attempt should be made to keep these subjects in the study and complete all subsequent study visits in the same way as subjects who are still on study drug. If this is not possible, subjects off study drug will have the option to be followed via limited assessments as defined in Section 6.7.2.

Subjects who have permanently discontinued study drug, reached kidney failure, or are no longer able to continue to attend clinic visits in-person, and have not withdrawn full consent will be asked to continue to participate in this study via remote assessments as defined in Section 6.7.3.

3.5. Discontinuation Criteria from Study

Subjects may discontinue from study for the following reasons:

- Death
- Pregnancy during the study; refer to [Appendix 6](#)
- Participation in another therapeutic clinical study
- Withdrawal of consent and refusal to allow any subsequent data collection, including passive methods. If a subject is amenable to any degree of limited follow-up or data collection, including passive methods, the subject must not be discontinued from the study
- Significant subject noncompliance with study drug administration, study procedures, or study requirements per judgement of the investigator
- The subject is lost to follow-up after exhaustion of all contact efforts until the global study end date; see Section 6.7.3.
- Investigator's decision to remove the subject from the study
- Discontinuation of the study by the Sponsor, a Regulatory Agency, or an IRB or EC

For subjects who discontinue from study for reasons other than death, withdrawal of full consent or loss to follow-up, the subject should complete the end of study (EOS) visit. Subjects who permanently discontinue study drug and study on the same day should complete the EOT visit and return to clinic for their EOT Follow-up visit 30 days (± 7 days) for assessments. If an ECG or STS was conducted at a previous visit within 24 weeks of the EOT/EOS visit, the assessment does not need to be performed at the EOT/EOS visit.

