6.7. Post End of Treatment Follow-up Assessments

Following permanent study drug discontinuation, subjects should remain on study and continue to attend all subsequent study visits in the same manner as subjects who are still on study drug for full assessments (see Section 6.7.1).

Alternative follow-up visits and assessments have been defined to ensure subjects remain on study through the global study end date. If a subject indicates the assessments or in-clinic visits have become burdensome, an alternative follow-up method should be implemented (see Sections 6.7.2 and 6.7.3).

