6.1.3. Analysis of the Primary Endpoint

The Primary Analysis Set for efficacy analyses is the Full Analysis Set.

Definition of Baseline

Baseline eGFR_{cr} for the primary analysis is defined as below:

- SEL arm: The average of the measurements at Visit C and Visit 1. This Baseline will also be referred to as post-run-in Baseline.

- Placebo arm: The average of the measurements at Visit A (enrollment) and Visit B. This Baseline will also be referred to as pre-run-in Baseline.

Estimand

The Treatment Policy estimand is defined as follows. This is the primary estimand for the primary endpoint.

- 1) Population: Subjects in the FAS. See definition of the FAS in Section 3.1.3.
- 2) Variable: Primary endpoint (eGFR_{cr} slope from treatment-specific Baselines through Week 84). See Section 6.1.1 for detailed definition of the primary endpoint.
- 3) Intercurrent events: Intercurrent events for this study include study treatment discontinuation and/or starting a concomitant medication (e.g. SGLT-2 inhibitors).

The occurrence of an intercurrent event is irrelevant. All observed values will be used regardless of occurrence of an intercurrent event.

- All observed values will be used regardless of occurrence of an intercurrent event (i.e, All available data defined above)
 - If a subject is lost to follow up, treat data as missing from the point of loss to follow-up onward
- 4) Population-level summary: eGFR_{cr} slope from treatment-specific Baselines through Week 84 in each treatment arm, and difference in eGFR_{cr} slope from treatment-specific Baselines through Week 84 between SEL and placebo treatment arms.

Main Estimator

A random slope model will be used to evaluate SEL treatment effect on eGFR_{cr} slope from treatment-specific Baselines through Week 84. The random slope model will have eGFR_{cr} change from treatment-specific Baselines at Weeks 4, 8, 12, 24, 36, 48, 60, 72 and 84 as outcome, and will include terms for eGFR_{cr} at treatment-specific Baselines as a continuous variable, pre-run-in Baseline UACR category (< 1500 mg/g vs. ≥ 1500 mg/g), concomitant use of SGLT-2 inhibitors at Randomization, treatment group, week, and treatment-by-week interaction. Within-subject variance covariance will be modeled as unstructured. If model convergence problems arise, other variance-covariance structures, such as Heterogeneous Toeplitz, will be considered and documented.

Sensitivity analyses of the eGFR_{cr} slope endpoint will include the following:

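### Protocol Section 3.5 lets an investigator end all study follow-up of a willing randomized subject for noncompliance with study drug, against Sections 3.4 and 6.7 and the treatment-policy estimand

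*Protocol*

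**What the plan says.** Protocol Section 3.5 opens its list with "Subjects may discontinue from study for the following reasons". The list includes "Significant subject noncompliance with study drug administration, study procedures, or study requirements per judgement of the investigator", entry into another therapeutic trial, and an open-ended "Investigator's decision to remove the subject from the study". The consent-withdrawal bullet carries a safeguard: if the subject accepts any limited or passive follow-up, "the subject must not be discontinued from the study". No other bullet repeats it. For exits other than death, full withdrawal of consent or loss to follow-up, "the subject should complete the end of study (EOS) visit". If drug and study stop on the same day, an EOT visit and a 30-day EOT follow-up visit are due instead. Appendix 2 schedules eGFR at all three.

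Section 3.4 gives the identical noncompliance reason for stopping study drug, then asks sites to do all they can to retain such subjects. Section 6.7 agrees: "Following permanent study drug discontinuation, subjects should remain on study and continue to attend all subsequent study visits". Section 6.7.2 sets a minimum of 12-weekly assessments that include eGFR. Section 6.7.3 adds remote contact about every 24 weeks, but only until a Section 3.5 reason applies or the study ends.

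SAP Section 6.1.3 defines a treatment-policy primary estimand: "All observed values will be used regardless of occurrence of an intercurrent event". Its only missing-data statement concerns subjects lost to follow-up.

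**The concern.** One behaviour, poor adherence to study drug, leads to two incompatible instructions. Sections 3.4 and 6.7 keep the subject under observation. Section 3.5 allows the investigator to end observation altogether, even when the subject would attend visits or take a telephone call.

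A treatment-policy estimand needs outcomes after treatment stops or falters. A discretionary exit tied to adherence removes the subjects whose later data it depends on. Exit is decided after randomization, and Protocol Section 1.3 releases eGFR from Week 4 onward to investigators, so the decision can be made knowing the subject's course. Measurements not taken cannot be recovered at the analysis stage.

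**Working it through.** **1. The plan's own figure, and whether this is a power problem.** Protocol Section 8.9.1 gives a slope difference of 3.7, SD 10 (both mL/min/1.73 m²/year) and one-sided alpha 0.15. Power = Φ(3.7 / (10·√(2/n)) − 1.036).
- n = 150 per arm: Φ(3.204 − 1.036) = 98.5% (plan: 99%).
- n = 127 per arm: Φ(2.948 − 1.036) = 97.2% (plan: 97%).

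Both reproduce. Assumed further losses of 5% or 10% on top of the plan's 15% leave 120 or 114 per arm and power of 96.6% or 96.1%. Precision is not the issue.

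**2. What is lost, and when.**

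| Stage | Source | Data |
|---|---|---|
| On study, adhering poorly | SAP 3.1.3, 6.1.3 | eGFR collected and used in the Full Analysis Set |
| At removal | Protocol 3.5, Appendix 2 | EOS eGFR, or EOT and 30-day eGFR |
| After the closing visits | Protocol 3.5, 6.7.3 | Nothing scheduled; the remote track has also ended |

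The primary slope runs through Week 84 (SAP 6.1.1), so an early removal can forfeit more than a year of visits.

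**3. Kidney Clinical Events.** Removal can decide how a subject is classified.
- SAP 6.2.2.1 counts a subject without sufficient measurements as having no event.
- SAP 6.2.1 counts an eGFR threshold value as an event when confirmation is missing because of study discontinuation.
- SAP 6.2.1 censors event-free early leavers at their last kidney assessment.

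The same discretionary act can therefore produce a non-event or an event, depending on its timing.

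**4. Direction of bias on the slope.** The SEL baseline is post-run-in, taken on drug. Stopping SEL has two opposing effects: loss of chronic benefit, and reversal of the acute fall (about 10% of baseline at Week 4 on 18 mg, Protocol 1.2.3.2.3; reversible after washout in the Phase 1b study, 1.2.3.1).

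To illustrate, take one SEL subject with the SAP's nine visits (Weeks 4 to 84) who stops at week s. Assume full loss of the 3.7/year benefit from then on and a rebound r of 0, 2 or 4 mL/min/1.73 m² (2 and 4 are 10% of an eGFR of 20 and 40). The departure from the on-drug line is d(w) = 0 for w ≤ s, and d(w) = r − 3.7(w − s)/52 for w > s. The least-squares slope of d on w/52, per year, is:

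| Stop week | r = 0 | r = 2 | r = 4 |
|---|---|---|---|
| 4 | −3.70 | −3.17 | −2.64 |
| 24 | −2.88 | −1.24 | +0.39 |
| 36 | −2.18 | −0.51 | +1.17 |
| 48 | −1.47 | +0.07 | +1.60 |

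Where the entry is negative, losing the off-drug values flatters SEL. Where it is positive, losing them penalises SEL. The sketch is for one subject, not the random slope model, and it ignores closing-visit values and removals on placebo.

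**5. Removal rate.** None is given. Protocol 1.2.3.2.2 reports study-drug discontinuation of 28.9% on SEL 18 mg and 22.4% on placebo in the earlier Phase 2 trial. That is stopping drug for any cause, not leaving the study. In the pooled SEL group, adverse events (18), ESKD (13) and consent withdrawal (13) account for 44 of 57, so all other reasons together come to 13/248 = 5.2%.

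**The case against.** The strongest reply is that Section 3.5 is permissive and retention is the default everywhere else. This stands as a limit on the point. A reader might infer that data from poor adherers are never collected, and the documents do not support that. Values up to removal are taken and analysed, closing eGFR is due, and the per-protocol exclusion for adherence below 80% presupposes such subjects have data. What is lost is follow-up after the closing visits, in those actually removed.

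A reader might also multiply an assumed removal fraction by 3.7 and report that SEL is overstated by, say, 0.19 or 0.37 mL/min/1.73 m²/year at 5% or 10%. That needs full reversion to the placebo slope from randomization, no rebound, no data from removed subjects and no removals on placebo. The documents support none of these, and step 4 shows the sign can reverse.

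Run-in also weakens the arm-dependent mechanism. The first acute fall occurs before randomization with values withheld, and seven consecutive doses are required before Visits C and 1. This reduces early differential removal but does not govern the later months.

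SAP Appendix 2 imputes off-treatment eGFR in the SEL arm. It predicts only the first change after stopping, from SEL subjects whose off-treatment values were collected, and feeds only sensitivity analyses. It does not replace later follow-up.

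**Conclusion.** The inconsistency is real and current. Section 3.5 allows a willing subject to be taken out of all follow-up for noncompliance with study drug. Sections 3.4 and 6.7 to 6.7.2 say subjects off drug should stay, and the primary estimand assumes they do. The remote track does not close the gap, because Section 6.7.3 defers to Section 3.5. The consequence is avoidable and possibly informative missing data on the primary slope, and event classification that can turn on an investigator's decision.

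No magnitude is claimed. The removal rate is unknown and the direction of bias is not fixed, so a bias in SEL's favour should not be asserted. The effect on power is small under the losses assumed in step 1. The conclusion rests on the text of the two documents, not on the illustration.

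**What to change.** This concerns data collection only; the treatment-stopping list in Section 3.4 is left as it is.

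- Reconcile Section 3.5 with Sections 3.4 and 6.7 to 6.7.3 and SAP Section 6.1.3 by removing noncompliance with study drug as a reason to end study follow-up.
- Extend the safeguard now confined to the consent bullet to what remains of the noncompliance bullet, to entry into another therapeutic study, and to investigator decision. A subject who still accepts any follow-up then moves to the limited track (6.7.2) or the remote track (6.7.3).
- Prefer the limited track where the subject accepts it. It keeps 12-weekly eGFR, whereas the remote track records survival, dialysis and transplantation but no eGFR.

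The cost is one protocol wording change. Both tracks already exist. The downside is that sites go on contacting a few reluctant subjects. SAP Section 4.1 already tabulates reasons for leaving the study by treatment group, which would show how often the route was used but would not recover the data.

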3.6. End of Study

The primary analysis of $eGFR_{cr}$ slope will be performed after all subjects in the ITT Analysis Set complete the Week 48 visit or discontinue from the study. The global study end date is defined as when the last randomized subject reaches 48 weeks and/or all subjects on study have completed end of study assessments and the 30 Day EOS Safety Follow-up visit.

CCI

[REDACTED]

[REDACTED]

[REDACTED]

[REDACTED]

[REDACTED]

[REDACTED]

[REDACTED]

CCI

[REDACTED]

[REDACTED]

[REDACTED]

CCI [REDACTED]

[REDACTED]

[REDACTED]

[REDACTED]

[REDACTED]

4. SUBJECT POPULATION

4.1. Number of Subjects and Subject Selection

This study will enroll approximately 300 subjects with T2DM and eGFR ranging from ≥ 20 mL/min/1.73 m² to < 60 mL/min/1.73 m² with albuminuria receiving standard of care therapy (ACEi or ARB, or intolerant to ACEi and ARB).

4.2. Inclusion Criteria

Subjects must meet *all* of the following inclusion criteria to be eligible for enrollment in this study:

- 1) Male or female between 18 (or \geq age of majority in each jurisdiction if different than 18) and 80 years of age, inclusive
- 2) Prior diagnosis of T2DM with diagnostic modalities as per local guidelines. Must have hemoglobin A1c (HbA1c) $> 6\%$ within 30 days prior to Enrollment (Visit A) or be on active treatment for T2DM for at least 6 weeks prior to Enrollment (Visit A)
- 3) eGFR value calculated by central laboratory utilizing samples collected during Screening and prior to Enrollment (Visit A) of ≥ 20 mL/min/1.73 m² to < 60 mL/min/1.73 m² with albuminuria as measured by UACR
 - a) eGFR values will be calculated using the Chronic Kidney Disease Epidemiology (CKD-EPI) Creatinine Equation (2009); UACR will be determined by urine collection, preferably early morning void. Subjects can have up to 3 eGFR and 3 UACR collections during the Screening period. Any one of the eGFR values and any one of the UACR values collected during Screening may be used to satisfy this inclusion criterion. Qualifying eGFR and UACR values do not need to be collected on the same day
 - b) eGFR and UACR must meet criteria a, b, or c

Criteria	eGFR (mL/min/1.73 m ²)	UACR (mg/g)
a	≥ 45 to < 60	≥ 600 to 5000
b	≥ 30 to < 45	≥ 300 to 5000
c	≥ 20 to < 30	≥ 150 to 5000

- 4) Treatment with either an ACEi or ARB as a single agent at the maximum labeled or tolerated dose deemed appropriate for the subject by the investigator and/or per local SOC for at least 6 weeks prior to Enrollment, with a stable dose for at least 2 weeks prior to Enrollment
 - a) Subjects not receiving an ACEi or ARB may be enrolled if there is documented intolerance to ACEi and ARB
 - b) Subjects receiving less-than-maximal dose of an ACEi or ARB may be enrolled if there is a documented reason that the maximum labeled dose of ACEi and ARB could not be reached
- 5) Subjects already receiving SGLT-2 inhibitors must be on a stable dose at least 2 weeks prior to Enrollment
- 6) For females of childbearing potential (unless permanently sterile or post-menopausal, as described in [Appendix 6](#)), a negative serum pregnancy test at Screening
- 7) For male and female subjects of childbearing potential who engage in heterosexual intercourse, agreement to abstain or use protocol specified method(s) of contraception as described in [Appendix 6](#)
- 8) Male subjects must refrain from sperm donation from the Screening visit through 30 days following the last dose of study drug
- 9) Female subjects must refrain from egg donation or harvest from the Screening visit through 30 days following the last dose of study drug
- 10) Subjects must refrain from blood product donation from the Screening visit through 30 days following the last dose of study drug
- 11) Mean systolic blood pressure (SBP) must be < 160 mmHg and mean diastolic blood pressure (DBP) must be < 100 mmHg taken at two time-points at least five minutes apart within 30 days prior to Enrollment (Visit A)
- 12) Required baseline laboratory data, analyzed by central laboratory, within 30 days prior to Enrollment (Visit A) as shown in the table below

Organ System	Parameter	Required Value
Hematologic	WBC, neutrophil, lymphocyte, and platelet count	$\geq 0.75 \times \text{LLN}$ to $\leq 1.5 \times \text{ULN}$
Hepatic	Serum total bilirubin	$\leq 1.5 \times \text{ULN}$
	Serum ALT	
	Serum AST	

Organ System	Parameter	Required Value
Pregnancy	β -HCG ^a	Negative
Infection	HIV ^b	Negative HIV antibody
	HBV	Negative HBsAg and negative HBc antibody or positive HBc and negative for HBV DNA by quantitative PCR
	HCV	Negative HCV antibody or negative viral RNA (if HCV antibody is positive)

a For women of childbearing potential only; serum β -HCG must be negative during Screening

b If screening test is positive, a negative confirmatory test will be required for eligibility

Abbreviations: β -HCG = beta human chorionic gonadotropin, ALT = alanine aminotransferase, AST = aspartate aminotransferase, DNA = deoxyribonucleic acid, LLN = lower limit of normal, HBc antibody = anti-hepatitis B core antibody, HBsAg = hepatitis B surface antigen, HBV = hepatitis B virus, HCV = hepatitis C virus, HIV = human immunodeficiency virus, PCR = polymerase chain reaction, RNA = ribonucleic acid, ULN = upper limit of normal, WBC = white blood count

- 13) Have either a normal 12-lead electrocardiogram (ECG) or an ECG with abnormalities that are not considered to be clinically significant by the investigator within 30 days prior to Enrollment (Visit A)
- 14) In the judgment of the investigator, participation in the study offers an acceptable benefit to risk ratio, taking into consideration the subject's current DKD status, medical condition, and the potential benefits and risks of alternative treatments for DKD
- 15) Willing and able to comply with scheduled visits, drug administration plan, laboratory tests, other study procedures, and study restrictions
- 16) Willing and able to give informed consent prior to any study specific procedures being performed

